## Incidence of 30 Day Return to Hospital Following Same Day Discharge Total Hip Arthroplasty

### BACKGROUND:

Same day discharge of primary total hip arthroplasty patients is becoming common in many large hospitals in Canada & the USA. At VGH/UBCH in 2017/18, a multidisciplinary committee was struck to create criteria for a same day discharge program at our hospital.

Despite the practice of same day discharge for hip arthroplasty becoming more prevalent across the country, there is a lack of specific evidence based criteria to establish which patients would be safe to be sent home same-day, and which should remain in hospital for a minimum of one over night stay. With the input of various clinicians, the multidisciplinary committee established an objective set of criteria that would establish patient eligibility for same-day discharge following primary hip arthroplasty at our institution. The program came to be known as the Short Term Accelerated Recovery (STAR) program and has been running since Oct 15, 2018.

The process for STAR enrollment begins with the attending surgeon earmarking the patient as potentially STAR eligible at the time of surgical booking. Following this, the patient is assessed by both Physiotherapy and Anesthesiology for eligibility to be a same day discharge or "STAR Patient". The criteria set by Anesthesiology is a document included with this submission. At the time of this submission, 78 patients have been enrolled as STAR Patients. Of these, 35 patients were deemed ineligible for STAR due to not fulfilling the preop criteria. Of the remaining 42 patients, 24 were discharged home same-day, and 19 were not able to be discharged home same-day due to perioperative issues on the day of surgery.

A failing of the program has been the lack of follow up with patients to know whether any complications or returns to hospital occurred during the first 30 days after surgery.

### OBJECTIVE:

As a Quality Assurance measure of safety for this program, we wish to know the rate of return to hospital for surgical related problems that occurred in this cohort in the first 30 days following surgery. Amongst the patients initially enrolled as STAR patients (presently 78 patients) we wish to compare the rate of return to hospital between those patients who were discharged the day of their surgery to those who spent at least their first night after surgery in hospital. Our objective is to see how the rates of return to hospital for surgical related complications or issues compares between those who went home same day as their surgery and those who didn't.

### METHODS:

#### Study Design:

This project is a retrospective cohort quality assurance study. Given that the criteria for enrollment in STAR is site specific and has not been established before, this project is designed to be a preliminary safety assessment that could inform future prospective studies on the

program's safety and inform the potential sample sizes needed for such studies. As well, the study would also expose the potential for a higher than expected return to hospital for same day discharge patients which may not otherwise have been known.

The Primary Goal is to discern how many same day discharge patients had return to hospital encounters during the first 30 days post surgery, and to compare this rate to that of patients who were not discharged on the same day as surgery.

Secondary Goals will be to compare return to hospital encounters within the first 7 days post surgery, as well as to compare and contrast the age and gender demographics of the cohorts studied.

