Incidence of 30 Day Return to Hospital Following Same Day Discharge Total Hip Arthroplasty

- Data Collection Spreadsheet Headings & Statistical
Analysis Plan -

[name], FRCPC
VGH/UBCH Dept of Anesthesiology & Perioperative Care
Vancouver General Hospital & UBC Hospital
Vancouver, BC, Canada

Oct 6, 2019

Incidence of 30 Day Return to Hospital Following Same Day Discharge Total Hip Arthroplasty

STAR STUDY SPREADSHEET COLUMN HEADINGS & STATISTICAL ANALYSIS PLAN:

A) SPREADSHEET COLUMN HEADINGS:

Data from chart reviews will be collected into the following five spreadsheets.

Spreadsheet 1 will be the De-identifier spreadsheet, the only data collection apparatus containing any personal identifiers. This spreadsheet will be retained only by the PI and stored on a password protected personal computer without any “off-site” or cloud based storage. Spreadsheet 1 information will be distributed to Research Personnel in paper form only.

Spreadsheet 2 will be an all patients list that will segregate patients into one of the three cohorts being studied.

Spreadsheet 3 will retain data from the “STAR Eligible & Discharged Same Day” cohort.

Spreadsheet 4 will retain data from the “STAR Eligible, NOT Discharged Same Day” cohort.

Spreadsheet 5 will retain data from the “NOT STAR Eligible” cohort.

The Data collection venue for de-identified Spreadsheets 2 to 5 will be Redcap (©).

1) De-Identifier:

Patient Study Number	MRN	Date of Surgery	Last Name	First Name	Date of Birth	Age	Gender

2) All Patient List:

Patient Study Number	Removed From STAR Pathway (Y or N)	Discharged On Day Of Surgery (Y or N)

3) Discharged Day of Surgery:

Patient Study Number	PACU Arrival Time	Discharge Home Time	Duration of Hospital Stay (min)	Hospital Re-encounter (Y or N)	Days Post-op at time of Re-encounter	Nature of Surgical Problem/Complication	Anesthesia Checklist Complete (Y or N)

4) NOT Discharged Day of Surgery:

Patient Study Number	Reason Not D/C'd Same Day - General	Reason Not D/C'd Same Day - Specific	Days In Hospital Post-Op	Hospital Re-encounter (Y or N)	Days Post-op at time of Re-encounter	Nature of Surgical Problem/Complication	Anesthesia Checklist Complete (Y or N)

5) Removed from STAR Pathway Prior to Surgery:

Patient Study Number	Reason for STAR Removal - General	Reason for STAR Removal - Specific	Days in Hospital Post-Op	Hospital Re-encounter (Y or N)	Days Post-op at time of Re-encounter	Nature of Surgical Problem/Complication	Anesthesia Checklist Complete (Y or N)

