
B) STATISTICAL ANALYSIS PLAN:

Statistical analysis will focus on the Primary and Secondary Outcomes (incidence of 30 and 7 day return to hospital encounters for surgical related assessment, complications &/or treatments respectively). Demographic data of patient age and gender will also be statistically analyzed.

Statistical analysis will be conducted with the aid of a Statistician affiliated with the UBC Department of Statistics, and the use of "R" software for statistical computations (© "The R Foundation"). Data will be reported as percentages or means +/- confidence intervals as appropriate.

Demographic data (age and gender) will be statistically compared between the three cohorts as follows. Age, being a numerical discrete variable, will be compared using Kruskal-Wallis Rank Sum Test. Gender, being a binomial variable, will be compared using Pearson's Chi-Squared test with Yates Correction for Continuity.

The Primary Outcome Statistical Analysis will be conducted as follows.

The two-tailed "null" (H_0) and "alternate" (H_A) hypothesis testing is as follows:

H_0 = Incidence of 30 day return to hospital not significantly different between compared groups

H_A = Incidence of 30 day return to hospital is significantly different between compared groups

Data from each of the cohorts will be plugged into the following three (A, B & C) 2 X 2 outcome tables:

Tables For Comparative Statistics:

A)

	Number of Patients with 30 Day Encounters or Complications	Number of Patients with NO 30 Day Encounters or Complications
Eligible & Same Day Discharged		
Eligible & NOT Same Day Discharged		

B)

	Number of Patients with 30 Day Encounters or Complications	Number of Patients with NO 30 Day Encounters or Complications
Eligible & Same Day Discharged		
Not Eligible for Same Day Discharge		

C)

	Number of Patients with 30 Day Encounters or Complications	Number of Patients with NO 30 Day Encounters or Complications
Eligible & Same Day Discharged		
Both: Eligible & NOT Same Day Discharged AND Not Eligible for Same Day Discharge		

The categorical dichotomous outcome data from each of these 2 X 2 tables will be assessed for statistically significant differences using Pearson's Chi-Squared test with Yates Correction for Continuity, unless expected values are less than 10 (with degrees of freedom of 1) in which case Fisher's Exact Test will be used. Statistical significance is set at $\alpha = 0.05$.

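### The 7-day secondary outcome runs from surgery, so patients kept overnight have less time in which to return; a descriptive discharge-anchored 7-day result should be reported beside it

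*Protocol*

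**What the plan says.** The protocol (Methods, Study Design) counts the 30-day primary outcome and the 7-day secondary outcome from surgery. The secondary goal is to "compare return to hospital encounters within the first 7 days post surgery". The SAP (section B) puts the number of patients with and without an event into three 2 x 2 tables. Same-day patients are compared with eligible patients kept in (Table A), with ineligible patients (Table B), and with both combined (Table C). The 7-day analysis reuses these tables with the 7-day rate.

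The protocol's Objective defines the comparators as "those who spent at least their first night after surgery in hospital". Its Background says how they came to stay: "35 patients were deemed ineligible for STAR due to not fulfilling the preop criteria", and "19 were not able to be discharged home same-day due to perioperative issues on the day of surgery".

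The SAP's column headings include "Days Post-op at time of Re-encounter" for all three cohorts. They include "Days In Hospital Post-Op" for eligible patients kept in, and the same item for ineligible patients. On reporting, the SAP says: "Data will be reported as percentages or means +/- confidence intervals as appropriate". The analysis section makes no use of length of stay and plans no 7-day result counted from discharge.

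**The concern.** A patient still in hospital cannot return to it. Length of stay defines the groups, so the lost time falls on the same side of every table. Same-day patients can return during nearly all of the 7 days. A comparator with a stay of L days can return only during the last 7 - L.

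This matters because of what the study is for. The protocol says that "the study would also expose the potential for a higher than expected return to hospital for same day discharge patients". With identical underlying risk, and counting only returns, the 7-day table is expected to show a higher rate in same-day patients. If comparators truly carry more risk, which their route into the group makes plausible, the same mechanism could hide that. The 7-day table alone cannot separate a difference in safety from a difference in time at risk, and the study's rates are meant to inform the design of later work.

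**Working it through.** **Plan's own figure.** There is none to reproduce: the documents state no 7-day rate, length of stay or power.

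**Inputs from the documents.** Windows of 7 and 30 days from surgery; a stay of at least one night for comparators; 24 same-day, 19 eligible but kept in, and 35 ineligible (sum 78); up to 120 patients; two-sided alpha 0.05. The Background speaks of 42 remaining patients, but 24 + 19 = 43 = 78 - 35, so I use the component counts.

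**Assumptions.** Stay L = 1, 2 or 3 days; same-day 7-day risk 5%; same-day patients leave at about day 0; the same hazard by day since surgery in both groups. That hazard is constant, or halves every 7 days, or halves every 3 days.

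**Window lost.** L/7 = 14%, 29%, 43% for L = 1, 2, 3. L/30 = 3%, 7%, 10%.

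**Apparent ratio with no true difference.** Let s be the share of the 0-7 day cumulative hazard that falls in (L, 7) when counting from surgery, or in (L, L + 7) when counting from discharge. Comparator risk = 1 - 0.95^s, and ratio = 0.05 / comparator risk. For a 2-day stay with constant hazard, s = 5/7 = 0.714, comparator risk = 3.60%, and ratio = 5.00/3.60 = 1.39.

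| Stay | Anchor | Constant | 7-day half-life | 3-day half-life |
|---|---|---|---|---|
| 1 day | surgery | 1.16 | 1.23 | 1.34 |
| 1 day | discharge | 1.00 | 1.10 | 1.25 |
| 2 days | surgery | 1.39 | 1.55 | 1.84 |
| 2 days | discharge | 1.00 | 1.21 | 1.57 |
| 3 days | surgery | 1.73 | 2.03 | 2.62 |
| 3 days | discharge | 1.00 | 1.34 | 1.97 |

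**Share of the bias removed by re-anchoring**, 1 - ln(ratio from discharge)/ln(ratio from surgery), 2-day stay: 100%, 56% and 26%.

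**In patients.** Scaling the present split to 120 gives 120 x 24/78 = 37 same-day, 120 x 19/78 = 29 eligible but kept in, 120 x 35/78 = 54 ineligible, and 120 x 54/78 = 83 comparators combined. With equal windows 83 x 0.05 = 4.15 comparator events are expected. A 2-day stay leaves 2.99, 2.68 or 2.26, a loss of 1.2, 1.5 or 1.9 events.

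**Effect on the test.** Exact rejection rate of two-sided Fisher at 0.05, 5% risk, 2-day stay, counted from surgery:

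| Table | Equal windows | Constant | 7-day half-life | 3-day half-life |
|---|---|---|---|---|
| A (37 v 29) | 1.1% | 0.6% | 0.6% | 0.6% |
| B (37 v 54) | 1.7% | 2.7% | 3.1% | 3.8% |
| C (37 v 83) | 2.0% | 4.1% | 5.0% | 6.7% |

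**What would cancel it.** A comparator hazard 1/s times higher: 1.40, 1.56 or 1.86 for a 2-day stay.

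**30-day table.** With a 2-day stay and an assumed 5% 30-day risk, the ratio is 1.07, 1.23 or 1.57 from surgery and 1.00, 1.21 or 1.57 from discharge. Re-anchoring would change almost nothing there.

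**The case against.** Much of the opposing case stands.

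- **Surgery is a proper time zero.** A reader might infer that the surgery anchor is an error, or that the 7-day analysis should be replaced. The documents do not support that. The Objective asks how return rates compare between those who went home and those who stayed. On that question, a problem managed in hospital without a return is part of what differs between the groups.
- **The planned 30-day table already shows about as little window loss as the proposed addition.** For a 2-day stay its ratios are 1.07, 1.23 and 1.57, against 1.00, 1.21 and 1.57 for the discharge-anchored 7-day result (5% risk assumed in each window). The addition therefore helps mainly with early returns.
- **The lost window may be partly offset.** The SAP's table columns join encounters with complications and do not say whether complications during the index stay count. If they do, comparators can have events before discharge. Elsewhere the SAP describes the outcome as return encounters, so the point is open.
- **The effect on the test is small.** Table C at 120 patients is the most affected. In Table A the rejection rate falls.
- **The bias makes same-day discharge look worse, which is the cautious direction.** A reader might infer that an excess of 7-day returns in same-day patients can be dismissed as an artefact. That goes too far, since it would mute the screen that the protocol describes.

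These arguments do not remove the fact that the plan collects length of stay and never uses it to interpret a comparison whose groups are defined by it. A discharge-anchored result chosen after seeing the data would also be less credible than one specified now.

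**Conclusion.** The point holds as a minor one. Counting the 7-day outcome from surgery takes time at risk of return from comparators only. By itself this raises the apparent 7-day rate in same-day patients relative to them. At 5% risk with no true difference, the apparent ratio is 1.16 to 1.73 for stays of 1 to 3 days under constant hazard. For a 2-day stay it reaches 1.55 or 1.84 if the hazard halves every 7 or 3 days. Stay, risk and timing are all assumed; the documents establish only that comparators stay at least one night.

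The distortion lies mainly in the reported rates rather than in the test. The net direction in the actual data is unknown, because comparators may carry higher underlying risk and index-stay complications may count. The planned analyses can stand. The 30-day primary loses only 3-10% of its window, against 14-43% at 7 days, and needs no change.

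**What to change.** Keep the surgery-anchored 30-day and 7-day outcomes. Add to the SAP:

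1. One prespecified descriptive 7-day proportion per group, with confidence interval, counted from index discharge: days post-op at re-encounter minus days in hospital post-op, with the same-day stay set to 0. No additional hypothesis test.
2. The comparators' length of stay, reported beside it.
3. A statement whether complications during the index stay count as events in the 2 x 2 tables.
4. A sentence that the surgery-anchored 7-day difference is to be interpreted together with length of stay and the discharge-anchored result. It should not say that the difference is not to be read as a safety signal.
5. The limits of the added result. It compares different recovery days (for a 2-day stay, post-op days 2-9 against 0-7). It only partly corrects risk that is concentrated early (about 26-56% of the bias for a 2-day stay with a 3- or 7-day half-life). It does not adjust for differences in underlying risk.

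The cost is one derived variable from columns already collected, one set of proportions and a few sentences. The planned 30-day chart search suffices for any stay up to 30 - 7 = 23 days. The downside is one more descriptive result that must be read with these limits.

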#### Patient Recruitment & Data Sources:

A list of all patients enrolled in the STAR Process is retained by the PI. Research Personnel will use this list to review STAR Patient's charts. This will include both the paper chart records at VGH and UBCH, as well as the BC Care Connect provincial online charts. Patients enrolled in STAR need to live within one hours drive of VGH and are instructed to return to the VGH Emergency Room if they have surgical related concerns after surgery. Nonetheless, patients living in the surrounding areas that are within an hour of VGH (eg. Burnaby or Surrey) may have occasion to visit their local hospital rather than return to VGH. It is for this reason that the BC Care Connect network will be accessed for each patient to see if any hospital encounters other than at VGH occurred during the first 30 days after surgery.

The chart records will be reviewed specifically looking for post surgical hospital encounters up to 30 days post hip arthroplasty. If a post surgical encounter is found on record, the nature of the encounter within the chart will be explored to discern whether the encounter was for a surgical related problem. If a post surgical encounter is found, data collected about this encounter will include the nature of the problem and how many days postop the encounter occurred. Sources of information for this data collection will be entirely by chart review. There will be NO patient contacts made for the purpose of data substantiation.

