#### INVESTIGATION TEAM:

The Principle Investigator in this study ([name]) is ultimately responsible for all matter of data collection and processing. All others collecting data will be either members of the Dept of Anesthesia at VGH & UBCH, or Medical Students from a Canadian University and trained by the Principle Investigator in the process of data collection. Any Medical Students involved in this project will be granted the right to participate in data collection by the Dept of Anesthesia prior to commencing.

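### The SAP's primary outcome depends on a surgical-relatedness call that is likely to be made with the discharge cohort known; the direction of any bias cannot be determined

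*Protocol*

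**What the plan says.** **The outcome.** The Protocol's Objective concerns returns for problems related to the surgery. Under Patient Recruitment & Data Sources, when an encounter is found, its nature is examined in the chart to "discern whether the encounter was for a surgical related problem". The SAP's Statistical Analysis Plan section defines the 30-day primary and 7-day secondary outcomes with the same restriction. The primary goal under Study Design does not carry it, and the column heads of the SAP's 2×2 tables refer to encounters or complications. Neither document gives a definition or code list for relatedness.

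**Who codes, and what they see.** "Research Personnel will use this list to review STAR Patient's charts", using the full paper and provincial online records. On the team, besides the principal investigator: "All others collecting data will be either members of the Dept of Anesthesia at VGH & UBCH, or Medical Students from a Canadian University". In the SAP, "Spreadsheet 2 will be an all patients list that will segregate patients into one of the three cohorts being studied". Re-encounter, post-operative day and nature of the problem are then entered on Spreadsheet 3, 4 or 5, according to cohort. On those sheets they stand beside the discharge time, the reason for not going home, or the reason for removal from the pathway.

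**Blinding.** The only blinding described (Protocol, Statistical Analysis) is of the statistician, to personal identifiers.

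**The concern.** A yes/no judgement without a written definition decides which returns count. If the person making it can see whether the patient went home the same day, borderline encounters may be classified differently by cohort. The groups are small and events are likely to be few, so a handful of such calls could decide the comparison.

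The Protocol wants the study to reveal a higher-than-expected return rate after same-day discharge and to inform the sample size of a later study. Differential coding would affect both uses, even if no test is significant. In addition, no sheet has a separate relatedness column, and the problem column is headed as a surgical problem or complication. An encounter judged unrelated might therefore leave no clear record that could be re-examined.

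**Working it through.** The plan gives no return rate, power or sample-size calculation, so there is no stated figure to reproduce. The check has two parts: whether coding is likely to be unmasked, and how much one call can matter.

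**1. Is coding likely to be unmasked?** Reviewers work from full charts, which show surgery and discharge timing. Outcome fields sit on cohort-labelled sheets. No masking, second reader or adjudication step is described. Neither document says outright that collectors know the cohort; it follows from these three facts together.

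**2. Group sizes.** The Protocol's Background reports 24 same-day discharges among 78 enrolled, and Number of Patients anticipates up to 120. If the share stays the same (assumption): 120 × 24/78 = 36.9, about 37 same-day, and 120 − 37 = 83 others. This is the SAP's Table C comparison.

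**3. Effect of one call on a rate.**
- Same-day group at 37: 1/37 = 2.7 percentage points.
- Same-day group at the reported 24: 1/24 = 4.2 points.
- Comparator at 83: 1/83 = 1.2 points.

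**4. Effect of one call on the test.** With 7 events in total, the expected same-day count is 7 × 37/120 = 2.2. That is below 10, so the SAP's rule selects Fisher's exact test. The two-sided p-value sums the hypergeometric probabilities no larger than that of the observed table.
- 5 versus 2 events: P(5) + P(6) + P(7) = 0.0249 + 0.0032 + 0.0002 = 0.028.
- 4 versus 2 events: P(4) + P(5) + P(6) = 0.0615 + 0.0099 + 0.0006 = 0.072.

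One same-day encounter coded the other way crosses the SAP's 0.05 threshold. The same happens at 7 versus 4 (p = 0.034) and 6 versus 4 (p = 0.067). The event counts are illustrations.

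**5. Either direction is possible.** Assume equal true encounter rates of 10% to 20% in both groups, but different shares coded as surgical. Rejection rates are exact, by enumerating both binomials at 37 and 83.

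| Share coded surgical, same-day vs others | Coded risk ratio | Rejection rate |
|---|---|---|
| 60% vs 60% | 1.00 | 2.2% to 3.3% |
| 80% vs 60% | 0.80/0.60 = 1.33 | 5.0% to 8.2% |
| 80% vs 40% | 0.80/0.40 = 2.00 | 12% to 23% |
| 40% vs 80% | 0.40/0.80 = 0.50 | 3.1% to 14.1% |

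Unequal coding can make same-day discharge look worse or safer than it is. All rates and coding shares are assumed.

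**The case against.** **The outcome may not need the judgement.** Read alone, the Study Design goal is an all-cause outcome, and the concern would then largely fall away. This stands as a reason to settle the definition. It does not dispose of the point, because the Objective, the data-collection section and the SAP all use the restricted outcome.

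**The raw data may already be planned.** The Protocol says the nature and timing of an encounter will be recorded when one is found, and the sheets hold a re-encounter flag separate from the problem description. The SAP also counts returns for surgical assessment, a broad category that leaves fewer borderline calls. This has some force, but the documents do not make clear that unrelated encounters are logged.

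**Larger problems exist.** This is a preliminary, chart-only project with non-randomised cohorts and no planned adjustment. Confounding may well outweigh a few codings. That is fair, and it limits the weight of the point, but coding is far cheaper to improve.

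**Stronger readings that the documents do not support.**
- A reader might infer that the coding would hide an excess in the same-day group. Nothing in the documents fixes the direction.
- A reader might measure the harm by lost power. With assumed true rates of 20% versus 5%, Fisher power at 37 versus 83 is 66%. It falls to 56%, 39% or 14% if 10%, 25% or 50% of same-day events alone are coded unrelated. But the same miscoding in both groups also lowers it, to 60%, 51% or 35%, so much of the drop is simply lost events and not the effect of knowing the cohort.
- A reader might infer that the collectors' department set the same-day criteria. The Background attributes eligibility to a multidisciplinary committee. It says "The criteria set by Anesthesiology is a document included with this submission", but that covers Anesthesiology's own part only.

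**Conclusion.** The point holds as a modest, inexpensive weakness in how the primary outcome is ascertained. The SAP's outcome depends on a relatedness judgement that is likely to be made with the cohort known, and the Protocol is inconsistent on whether that judgement belongs in the outcome.

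At about 37 versus 83 patients, one same-day call is worth 2.7 points and can move a result across 0.05. The size rests on the same-day share staying at 24/78, on accrual reaching 120, and on illustrative event counts. That collectors are unmasked is an inference from the layout and from the absence of any masking step.

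A reader might also infer that the existing team can eliminate the bias. That goes too far: the number of collectors is not given, the abstractor sees the full chart, and encounter notes may reveal the discharge day.

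**What to change.** 1. Reconcile the primary goal under Study Design with the Objective, Patient Recruitment & Data Sources and the SAP, so that one definition of a qualifying return applies throughout.
2. Replace the re-encounter columns in Spreadsheets 3 to 5 with one encounter sheet for all patients, keyed by study number and without discharge status. Log every hospital encounter to day 30, with its day and presenting problem. Add a separate yes/no column for surgical relatedness, completed before the Spreadsheet 2 cohort flags are merged. Where feasible, an existing team member who did not abstract that chart should complete it.
3. Report all-cause 30-day and 7-day returns in the same 2×2 tables as a sensitivity analysis, since these need no relatedness judgement.

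**Cost.** Rearranged REDCap columns, a short coding pass over a small number of encounters, and one more set of tables. The charts are being reviewed in any case, and no patient contact is needed. Masking will be imperfect; the all-cause analysis shows how far the conclusion depends on the coding that remains.
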